# **SYNOPSIS**

Protocol Number:	APD811-003		
Title:	A Randomized, Double-blind, Parallel-group, Placebo-controlled Phase 2 Trial of APD811, an Oral IP Receptor Agonist, in Patients with Pulmonary Arterial Hypertension		
Study Phase:	2		
Name of Drug:	APD811		
Indication:	Pulmonary Arterial Hypertension		
Sponsor:	Arena Pharmaceuticals, Inc. [name]		
Name of Sponsor Contact:			
Name of Principal Investigator:	Multicenter		
Medical Monitor:			
Scientific Expert:			
Dosage:	The starting dose of APD811 will be 0.01 mg b.i.d. The dose of APD811 will be titrated according to patient tolerability. Available dosage forms include 0.01, 0.02, 0.03, 0.04 mg, and 0.10 mg.  If the initial dose is tolerated (0.01 mg b.i.d.), then the dose will be increased in the following fashion at subsequent visits: 0.02 mg b.i.d., 0.03 mg b.i.d., 0.04 mg b.i.d., 0.06 mg b.i.d., 0.08 mg, 0.1 mg b.i.d.,		

	0.2 mg b.i.d and 0.3 mg b.i.d. The dose may be escalated to a possible maximum total daily dose of 0.6 mg (0.3 mg b.i.d.) pending tolerability.  If a dose is not tolerated, the study drug may be decreased to the provious dose level. If the initial dose of 0.01 mg b i.d. is not			
	previous dose level. If the initial dose of 0.01 mg b.i.d. is not tolerated, dosing may be decreased to 0.01 mg q.d.			
Concurrent Control:	Matching placebo			
Route and Formulation:	Oral, liquid-filled, hard-gelatin capsules			
Objectives:	Primary: The primary objective of the study is to assess the hemodynamic effects of APD811 and the effect of APD811 on 6MWD in patients with PAH after 22 weeks of treatment including an initial dose titration period of up to 9 weeks.			
	Secondary: The secondary objectives of the study are:  • to assess the safety and tolerability of APD811  • to assess the effect of APD811 on clinical worsening			
	Exploratory: Exploratory objectives of the study are:  • to assess the effect of APD811 on levels of BNP and			
	NT-proBNP after 22 weeks of treatment  • to assess change in WHO/NYHA functional class			
	
 
to evaluate the pharmacokinetics (Cmin and presumptive Cmax of oral APD811
 
			
	
 
to evaluate the effects of APD811 on systemic vascular resistance (SVR)
 
			
Study Design:	The study will be conducted as a placebo-controlled, randomized (2:1, APD811:placebo), 22 week double-blind study which will include a dose titration period of up to 9 weeks. An additional transition period of 3 weeks (±1 week) will occur for those patients who elect to enroll into the open-label extension study, APD811-007. Patients that do not continue in the extension study will have a 3-week follow-up visit. Approximately 60 patients with PAH will be enrolled.			
	Safety will be assessed by the Safety Monitoring Committee (SMC). The SMC will review safety data including adverse events, blood pressure and heart rate periodically, in order to ensure patient safety and determine an appropriate dose titration regimen.			

To be eligible to enroll in the extension study APD811-007, patients must complete study APD811-003. Additionally, placebo treated patients who discontinue study drug treatment due to clinical worsening in APD811-003 will be permitted to enroll in APD811-007, upon approval of the medical monitor, provided that all end of study procedures including right heart catheterization are performed per protocol.

Patients will be receiving concomitant oral disease-specific PAH therapy consisting of an endothelin receptor antagonist (ERA) and/or an agent acting on the nitric oxide pathway, a PDE5 inhibitor or a soluble guanlyate cyclase stimulator, provided the dose has remained stable for at least 3 months prior to the start of Screening. Patients should continue the same dose and regimen of these medications for the duration of the study.

The use of the following therapies, which may affect PAH, are permitted:

- Vasodilators (including calcium channel blockers), digoxin, spironolactone, or L-Arginine supplementation; if on a stable dose for at least 1 month prior to the start of Screening and should remain unchanged during the study.
  - Doses of spironolactone and digoxin may be held or reduced as necessary to protect the patient's safety. Doses may not be increased in the month before Day 1 and during the controlled study.
- Diuretics may be dosed as clinically indicated throughout the study.
- Intravenous inotropes within 1 month of starting Screening are not permitted.

In an attempt to maintain balance across treatment groups, the following stratification factor will be utilized during patient randomization:

• Baseline WHO/NYHA Functional Class (Class II vs. III or IV)

If a patient's participation in the study is discontinued early, all end of study (EOS) safety and efficacy evaluations are to be performed as part of the Week 22/Early Termination visit. The EOS visit for early terminations will be followed by a follow-up visit to ensure appropriate patient safety at Week 25. If the patient is unable to return for the follow-up visit, AE and concomitant medication follow-up may be conducted by telephone.

Study Site:	Multiple centers in United States, Europe, and Australia.		
Patient Population:	Up to 60 patients with PAH will be studied.		
	All women, regardless of childbearing potential, must have a negative pregnancy test at Screening (serum hCG) and on Day 1 (urine dipstick) of the dose titration period and periodically throughout the study (serum hCG).		
	Males and females of childbearing potential must use adequate means of contraception and must agree not to participate in a conception process (i.e., active attempt to become pregnant or to impregnate, sperm donation, in vitro fertilization) for 1 month after the last dose of study drug.		
Eligibility:	Key Inclusion Criteria:		
	
 
Males or females aged 18-75 years, inclusive
 
		
	
 
Symptomatic WHO Group 1 PAH classified by one of the following subgroups:
 
		
	- Idiopathic pulmonary arterial hypertension (IPAH);		
	- Heritable pulmonary arterial hypertension (HPAH);		
	- Drugs and toxins induced;		
	
 
Associated with (APAH); specifically connective tissue diseases, HIV infection and congenital heart disease
 
		
	Has had the diagnosis of PAH confirmed by cardiac catheterization		
	Has WHO/NYHA functional class II- IV symptomatology		
	
 
Previously diagnosed with PAH and on stable oral disease- specific PAH therapy with either an ERA and/or an agent acting on the nitric oxide pathway, i.e. a PDE5 inhibitor or a soluble guanlyate cyclase stimulator. Stable is defined as no change in dose within 3 months of the start of Screening and for the duration of the study.
 
		
	
 
Has 6MWT distances of 100-500 m, and within 15% of each other on 2 consecutive tests done on different days at Screening
 
		
	
 
Has pulmonary function tests (PFTs) within 6 months prior to the start of Screening with no evidence of significant parenchymal lung disease
 
		
	
 
Has a ventilation-perfusion (V/Q) lung scan or pulmonary angiogram within 5 years prior to Screening and concomitant with or following diagnosis of PAH that shows no evidence of thromboembolic disease
 
		

	7	
	• If on vasodilators (including calcium channel blockers), digoxin, spironolactone, or L-Arginine supplementation; the patient must be on a stable dose for at least 1 month prior to the start of Screening	
	Key Exclusion Criteria:	
	Newly diagnosed with PAH and on no disease-specific PAH therapy	
	
 
Previous participation in any clinical study with an investigational drug, biologic, or device within 2 months prior to the Screening visit
 
	
	
 
Acutely decompensated heart failure within 1 month prior to start of Screening
 
	
	
 
Systolic blood pressure <90 mm Hg at Screening
 
	
	
 
Evidence or history of left-sided heart disease and/or clinically significant cardiac disease
 
	
	
 
Use or chronic administration (defined as >30 days) of a prostacyclin or prostacyclin analogue within 3 months of Screening
 
	
	
 
Any previous use of a prostacyclin or prostacyclin analogue that was stopped for safety or tolerability issues associated with pharmacology/mechanism of action
 
	
	• Other severe acute or chronic medical or laboratory abnormality that may increase the risk associated with study participation or investigational product administration or may interfere with the interpretation of study results and, in the judgment of the investigator, would make the patient inappropriate for entry into this study	
Duration per Patient:	~29 weeks: 4 weeks for screening, a 22 week treatment period including a dose titration period of up to 9 weeks, followed by a 3 week follow-up visit. Patients will stay on treatment through the follow-up visit if continuing into the open-label extension study. For patients not continuing into the open-label extension study, treatment will be discontinued at the end of the treatment period.	
Patient Assignment:	Patients will be randomly allocated to APD811 or placebo in a 2:1 ratio.	
Sample Size:	Up to 60 patients.	
Efficacy Endpoints:	Efficacy will be assessed by measurement of pulmonary vascular resistance (PVR) obtained on RHC, measurement of B-type natriuretic peptide (BNP), N-terminal pro-brain natriuretic peptide (NT-proBNP) levels and six-minute walk test (6MWT).	

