Study drug administration h,i	→ j						
Six-minute walk test k	X	X	X	X	X		
Right heart catheterization				X l			

<sup>a Reference to pre-dose and post-dose activities in this schedule apply to the morning dose of study drug.

For patients who terminate early from the study and is unable to return for the follow-up visit at Week 25, AE and concomitant medication follow-up may be conducted by telephone.

<sup>c Patients should have all assessments including RHC, 6MWT and BNP/NT-proBNP completed prior to entering the transition period.

d Safety ECGs should be completed **pre-dose**.

<sup>e Clinical laboratory tests will include hematology, serum chemistry, coagulation, and urinalysis. Clinical laboratory tests will be completed **pre-dose**.

Serum pregnancy test will be completed **pre-dose** at each visit during the treatment period.

Vital sign measurements (blood pressure, heart rate, respirations, body temperature, and pulse oximetry, taken in supine position after 5-minute rest) will be taken **pre-dose**.

<sup>h Study drug should be taken with food.

On days with scheduled study visits, patients should **not** take their morning dose of study medication at home in order to complete pre-dose study procedures.

Patients entering the APD811-007 study will remain on current dose through the transition period. Patients who do not continue into the APD811-007 study will discontinue study medication at Week 22 visit but not prior to undergoing the final RHC, and will return for follow-up visit at Week 25; if the patient is unable return for the follow-up visit, AE and concomitant medication follow-up may be conducted by telephone.

<sup>k 6MWT should be completed **pre-dose** at approximately the same time of day at each designated visit.

			Transition Period			
Evaluation a		Treatment Period	End of Study (EOS) Visit	Follow-up Visit (start of OLE) ±1 week b		
Study Week	10	14	18	22 c	25	
Day	70	98	126	154	175	
BNP/NT-proBNP m	X			X	X	
Pharmacokinetic blood sample n	X	X	X	X		
WHO/NYHA functional class assessment o	X	X	X	X	X	
Assessment of clinical worsening	X	X	X	X	X	
Adverse event monitoring	+					
Concomitant medication monitoring	+				—	

RHC will be performed as part of Week 22 end-of-study procedures.

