# 6.13.2 Serious Adverse Events and Expedited Reporting of Adverse Events

A Serious Adverse Event (SAE) is any untoward medical occurrence that at any dose results in the following outcomes:

- Death
- Is Life-Threatening
- Required/Prolonged Hospitalization
- Disability/Incapacity
- Congenital Anomaly/Birth Defect
- Important Medical Event

SAEs will be captured from the time of screening to 30 days after the dose of study drug, and will be monitored until resolution or stabilization.

An important medical event that may not result in death, be life-threatening, or require hospitalization may be considered a SAE when, based upon appropriate medical judgment, it may jeopardize the patient and may require medical or surgical intervention to prevent one of the outcomes listed in this definition. Examples of such a medical event includes allergic bronchospasm requiring intensive treatment in an emergency room or at home, blood dyscrasias, or convulsions that do not result in in-patient hospitalization, or the development of drug dependency or drug abuse.

Elective hospitalization and/or surgery for clearly pre-existing conditions (for example a surgery that has been scheduled prior to the patient's entry into the study) will not be reported as a SAE. All other hospitalizations, including elective hospitalizations for any condition that was not pre-existing, will be reported as a SAE.

All SAEs, whether or not considered related to study treatment, must be reported to the sponsor Contact within 24 hours of becoming aware of the event. In addition, a completed report using the sponsor's SAE form must be submitted within 24 hours of notification to:

Arena Drug Safety and Pharmacovigilance Arena Pharmaceuticals, Inc. [name]

Other situations as defined in ICH Topic E2A, 21 CFR§ 312.32, and EU Volume 10 also qualify for expedited reporting. In these situations the process will be as detailed for SAEs above:

- Serious adverse events which could be associated with the trial procedures;
- Serious adverse events and adverse events of special interest that could materially influence the benefit-risk assessment of a medicinal product, such as: a clinically important increase in the rate of a serious suspected adverse reaction over that listed in the investigator brochure.

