Patients who become pregnant during the study will be discontinued immediately. Although not considered a SAE or AE, pregnancies occurring during the period of study drug administration (Day 1 of the dose titration period to Week 25/ Follow-up) until 30 days after the last dose of study drug should be reported to the sponsor Contact and IRB/IEC in the same manner as a SAE.

Pregnancies will be followed every trimester through the first well baby visit. For female partners who become pregnant by male study patients during the course of the study, reasonable efforts will be made to collect information on the partner's pregnancy through the first well baby visit as provided by the male study patient.

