#### 6.16 Allowable Visit and Procedure Windows

The following are the allowable windows for specific study visits and procedures during the 9-week dose titration period:

- Screening: within 28 days prior to dosing on Day 1
- Study visits (Weeks 1-9): ± 1 day
- Study visits (Weeks 10-22): ± 3 days
- Week 25 follow-up visit: ± 1 week
- Vital signs: ± 15 min
- Blood pressure and heart rate:  $\pm 15$  min
- Safety labs (excluding urinalysis): 15 min
- Baseline ECG: within 2 hours prior to dosing on Day 1
  - all other ECGs:  $\pm 15$  min
- Blood draws for PK samples:
  - time points up to 4 hours:  $\pm$  15 min

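### For patients who stop early, the only contact after the termination visit is written as Week 25 and not timed from the last dose, so it can fall well outside the 30-day safety window

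*Protocol*

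**What the plan says.** **Early stoppers.** The protocol synopsis (Study Design) requires that all "end of study (EOS) safety and efficacy evaluations are to be performed as part of the Week 22/Early Termination visit". It continues: "The EOS visit for early terminations will be followed by a follow-up visit to ensure appropriate patient safety at Week 25". Footnote b to Table 2 uses the same time point: "For patients who terminate early from the study and is unable to return for the follow-up visit at Week 25", adverse event and concomitant medication follow-up may be done by telephone. The synopsis gives the same substitute: "If the patient is unable to return for the follow-up visit, AE and concomitant medication follow-up may be conducted by telephone". The call replaces the visit and is not an extra contact.

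**The visit date.** Table 2 puts Week 22 at Day 154 and Week 25 at Day 175. Section 6.16 gives the tolerance: "Week 25 follow-up visit: ± 1 week".

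**A second description.** The synopsis also says, without separating completers from early stoppers: "Patients that do not continue in the extension study will have a 3-week follow-up visit". Section 7.4.3.2 places the Week 25 visit after a three-week (± 1 week) transition period.

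**The collection windows.** Section 6.13.1 continues adverse event monitoring for up to 30 days after study medication. Section 6.13.2 states: "SAEs will be captured from the time of screening to 30 days after the dose of study drug". For pregnancies the same section covers the period "until 30 days after the last dose of study drug should be reported". Only the pregnancy sentence names the last dose; I read the other two the same way.

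The SAP synopsis and SAP Appendix 2 repeat the synopsis sentences and the footnote, so the SAP does not settle the matter.

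**The concern.** The visit is tied to the calendar of the trial, whereas the collection windows are tied to the patient's own dosing. The two agree only for patients who stop near Week 22. For anyone who stops much earlier, the window opens and closes with no scheduled contact between the termination visit and its end. Events in those weeks then come to light through spontaneous reports or through recall at a visit that may be months later.

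This matters because safety and tolerability is a secondary objective and each patient is titrated to tolerance, so stops for intolerance are foreseeable. Section 1.1.3 reports that a single 0.2 mg dose was poorly tolerated by volunteers. Clinical worsening (Section 6.9) also counts fatal treatment-emergent events up to 14 days after discontinuation, so contact after stopping touches a secondary efficacy endpoint too. Under the literal reading such a death might be learned of late. The primary PVR comparison is not affected.

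**Working it through.** **1. The plan's own calendar.** Screening 4 + treatment 22 + follow-up 3 = 29 weeks, as stated under Duration per Patient. Week 22 = 22 × 7 = Day 154 and Week 25 = 25 × 7 = Day 175, as in Table 2. With ± 7 days, Week 25 spans Days 168 to 182.

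**2. Literal reading, early stoppers.** For a last dose on Day D, the gap is the visit day minus D. It exceeds 30 days when D is less than the visit day minus 30:

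| Visit held on | Outside the window if last dose is before |
|---|---|
| Day 168 | 168 − 30 = Day 138 |
| Day 175 | 175 − 30 = Day 145 |
| Day 182 | 182 − 30 = Day 152 |

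Gaps to Day 175:

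| Last dose | Window closes | Gap |
|---|---|---|
| Day 14 | Day 44 | 161 days (23 weeks) |
| Day 63 | Day 93 | 112 days |
| Day 126 | Day 156 | 49 days |

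**3. What share of early stoppers?** The documents do not say when patients drop out, so each row below is an assumption. Let c be the threshold day from step 2.

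| Assumed timing of last dose | Formula | Visit Day 168 | Day 175 | Day 182 |
|---|---|---|---|---|
| Uniform over Days 1–153 | (c − 1)/153 | 90% | 94% | 99% |
| Constant hazard, 30% lost by Day 154 | [1 − 0.7^(c/154)]/0.3 | 91% | 95% | 99% |
| None in titration (Days 1–63), rest uniform over Days 64–153 | (c − 64)/90 | 82% | 90% | 98% |
| 75% in titration, rest uniform over Days 64–153 | 0.75 + 0.25 × (c − 64)/90 | 96% | 98% | 99% |

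For example, uniform timing with a Day 175 visit gives 144/153 = 94%. The lowest value in the table is 82%.

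**4. Alternative reading, three weeks (± 1 week) after the termination visit.** The contact falls 14 to 28 days after that visit. The visit's own lag after the last dose is not stated. The contact stays within 30 days if the lag is no more than 30 − 28 = 2 days at the late end, 30 − 21 = 9 days nominally, or 30 − 14 = 16 days at the early end.

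**5. Completers not entering APD811-007.** They stop at Week 22, Day 154, so the window closes on Day 184. The visit on Days 168 to 182 comes 14 to 28 days after the last dose, which is 16 to 2 days before closure (9 days nominally). If the ± 3 days on Week 22 are added, the interval runs from 168 − 157 = 11 to 182 − 151 = 31 days, so only the extreme corner passes day 30.

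**6. Completers entering APD811-007.** They remain on drug through Week 25 (Sections 3.1 and 5.6.2), so no post-dose window has opened.

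**The case against.** The strongest reply is that Week 25 is a visit label. The synopsis calls the stopping visit Week 22/Early Termination whatever the actual day, and Week 25 could likewise name the next visit, three weeks on. The general synopsis sentence and Section 7.4.3.2 support this, and under it the long gaps disappear. The reading is possible. It does not settle the matter, because the two places that speak specifically of early stoppers both say Week 25 and neither mentions the last dose. One site could make contact at three weeks and another at five months.

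A reader might infer that early stoppers have no scheduled safety contact at all. The documents do not support that. The Early Termination visit carries adverse event recording, laboratory tests, ECG, serum pregnancy test and physical examination (Sections 6.15.1, 7.4.3 and 7.4.3.1). It is a real contact, though a visit at stopping cannot observe the 30 days that follow.

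A reader might also infer that harm after stopping goes unfollowed. That is too strong. The collection duty stands, patients may report at any time (Section 6.13.1), and those withdrawn for a medical reason stay under the study physician's supervision (Section 6.15.1). That last provision gives no contact date and does not cover other withdrawals. Section 6.13.8 follows events already present at Week 25; it does not schedule a search for new ones.

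For completers the objection largely succeeds. A visit at three weeks does not contradict a 30-day reporting duty. The half-life in Section 1.1.3 is at most 26.4 hours, so five half-lives are 5 × 26.4 = 132 hours, or 5.5 days, well before the earliest nominal visit at day 14.

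**Conclusion.** The point holds as a conflict in the timing of follow-up. On the literal reading, no scheduled contact after the termination visit falls inside the 30-day window for a last dose before Day 138 to 152. The loss is in active, scheduled ascertainment. The completer shortfall is minor and confined to those not entering the extension.

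The size rests on three assumptions: that sites follow the Week 25 wording, that all three windows run from the last dose, and a dropout pattern. About 94% is the figure for uniform stopping, and the patterns tried give 82% to 99%.

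Two further inferences are not supported. The sample size section allows for up to 30% dropout before a repeat catheterization, and 0.30 × 60 = 18. That is a planning allowance, not a count of early stoppers; some of these will have the termination catheterization and so fall outside it. Nor do the documents give a figure for how stops would divide between arms. More intolerance stops on active drug are plausible, but a differential loss of safety data cannot be quantified from the plan.

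This is an inexpensive improvement to safety ascertainment and does not threaten the efficacy inference.

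**What to change.** Reconcile the two synopsis sentences, Table 2 with its footnote b, Section 6.16 and Section 7.4.3.2. For every patient not entering APD811-007, the existing follow-up visit, or the telephone contact already allowed in its place, should be timed from the last dose, using the three weeks ± 1 week that the protocol already states. Sections 6.13.1 and 6.13.2 should name the last dose as the start of the 30 days, and the SAP synopsis and Appendix 2 should match.

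Optionally, add one short telephone check for adverse events, serious adverse events and pregnancy when the 30-day window closes. That would cover the 2 to 16 days left after the re-timed contact.

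The Week 25 contact should not be dropped unless the re-timed contact replaces it.

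The cost is wording changes and at most one extra call per patient not entering the extension. Treatment and the efficacy analysis are unchanged.
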